1.0 OVERVIEW OF STUDY DESIGN

The FC-9 study is designed as a phase II, open label, single arm study of the dual immune checkpoint blockade with the combination of durvalumab and tremelimumab following hypofractionated palliative radiation in patients with microsatellite stable (MSS) metastatic colorectal cancer (mCRC) who have progressed on chemotherapy. The primary aim is to determine the anti-tumor efficacy of the dual immune checkpoint blockade with durvalumab plus tremelimumab. The secondary aims are to determine the clinical benefit rate, duration of response, tolerability and correlates of response. Tumor response at unirradiated target lesions will be measured at baseline and every 2 cycles using RECIST 1.1.

[figure not shown]
Following three doses of hypofractionated palliative radiation (Days -2, -1, and Day 0 prior to Cycle 1), patients will receive the combination of tremelimumab (75 mg IV infusion) and durvalumab (1500 mg IV infusion) on Day 1 for 4 cycles. Beginning with Cycle 5 through Cycle 24, patients will receive durvalumab alone (1500 mg/IV infusion) on Day 1 of each 28 day cycle.

Toxicity will be graded according to the National Cancer Institute (NCI) Common Terminology Criteria for Adverse Events version 4.0.

The sample size will be between 12 and 21 evaluable patients. Patients who complete both Cycle 1 and Cycle 2, and undergo the first restaging scan after Cycle 2 for the determination of tumor response will be determined evaluable. Non-evaluable patients will be replaced. Twelve evaluable patients will be treated in the first stage of the study. If there are no responses among the 12 evaluable patients, the study will be terminated. If the study goes on to the second stage, a total of 21 evaluable patients will be studied. If the total number responding is less than or equal to 2, the combination will be rejected. If 3 or more responses are observed after the second stage of the study, the combination will be considered for further study.

Submission of tumor tissue and blood samples for FC-9 correlative science studies will be a study requirement for all patients. Requirements will include archived tumor samples from the diagnostic biopsy; additional biopsies of fresh tissue from an accessible lesion prior to radiation therapy and after 2 cycles of study therapy; and blood sample collections.

Figure 1
FC-9 Schema

‡Hypo-fractionated stereotactic body radiation therapy (SBRT)

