***Tremelimumab cycles 1-4**

- Tremelimumab: 75 mg IV infusion on **Day 1** of Cycle 1 through Cycle 4 (4 doses total).

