A population PK model was developed for durvalumab using monotherapy data from a Phase 1 study (study 1108; N = 292; doses = 0.1 to 10 mg/kg Q2W or 15 mg/kg Q3W; solid tumors). Population PK analysis indicated only minor impact of body weight (WT) on PK of durvalumab (coefficient of ≤ 0.5). The impact of body WT-based (10 mg/kg Q2W) and fixed dosing (750 mg Q2W) of durvalumab was evaluated by comparing predicted steady state PK concentrations (5th, median and 95th percentiles) using the population PK model. A fixed dose of 750 mg was selected to approximate 10 mg/kg (based on median body WT of approximately 75 kg). A total of 1000 patients were simulated using body WT distribution of 40–120 kg. Simulation results demonstrated that body WT-based and fixed dosing regimens yield similar median steady state PK concentrations with slightly less overall between-subject variability with fixed dosing regimens.

Similarly, a population PK model was developed for tremelimumab using data from Phase 1 through Phase 3 (N = 654; doses = 0.01 to 15 mg/kg Q4W or Q90D; metastatic melanoma). Population PK model indicated minor impact of body WT on PK of tremelimumab (coefficient of ≤ 0.5). The WT-based (1 mg/kg Q4W) and fixed dosing (75 mg/kg Q4W; based on median body WT of approximately 75 kg) regimens were compared using predicted PK concentrations (5th, median and 95th percentiles) using population PK model in a simulated population of 1000 patients with body weight distribution of 40 to 120 kg. Similar to durvalumab, simulations indicated that both body WT-based and fixed dosing regimens of tremelimumab yield similar median steady state PK concentrations with slightly less between-subject variability with fixed dosing regimen ([Wang 2014](#)).

A fixed dosing approach is preferred by the prescribing community due to ease of use and reduced dosing errors. Given expectation of similar pharmacokinetic exposure and variability, we considered it feasible to switch to fixed dosing regimens. Based on average body WT of 75 kg, a fixed dose of 1500 mg Q4W durvalumab (equivalent to 20 mg/kg Q4W), and 75 mg Q4W tremelimumab (equivalent to 1 mg/kg Q4W); is included in the current study.

Fixed dosing of durvalumab and tremelimumab is recommended only for patients with > 30kg body weight due to endotoxin exposure. Patients with a body weight less than or equal to 30 kg should be dosed using a weight-based dosing schedule.

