9.2 Durvalumab (MEDI4736)

9.2.1 *Description*

Durvalumab, a human IgG1 kappa monoclonal antibody directed against PD-L1, contains a triple mutation in the constant domain of the IgG1 heavy chain that reduces binding to C1q and the Fcγ receptors.

9.2.2 *Formulation*

Durvalumab will be supplied as a 500 mg vial solution for infusion after dilution. The solution contains 50 mg/mL durvalumab, 26 mM histidine/histidine-hydrochloride, 275 mM trehalose dihydrate, and 0.02% (weight/volume) polysorbate 80; it has a pH of 6.0. The nominal fill volume is 10 mL. Durvalumab must be used within the individually assigned expiry date on the label.

9.2.3 *Toxicity*

Refer to the current durvalumab (MEDI4736) IB for toxicity information.

9.2.1 *Contraindications*

The use of durvalumab is contraindicated in patients who are pregnant or nursing.

9.2.2 *Concomitant medications and other substances*

No formal drug-drug interaction studies have been conducted with durvalumab. There are no known clinically significant interactions of durvalumab with other medicinal products.

9.2.3 *Preparation*

The dose of durvalumab for administration must be prepared using aseptic technique. Total time from needle puncture of the durvalumab vial to the start of administration should not exceed 24 hours at 2°C to 8°C (36°F to 46°F) or 4 hours at room temperature. If total time exceeds these limits, a new dose must be prepared from new vials. Durvalumab does not contain preservatives, and any unused portion must be discarded.

A dose of durvalumab (1500mg) will be administered using an IV bag containing 0.9% (w/v) saline or 5% (w/v) dextrose with a final durvalumab concentration ranging from 1 to 20 mg/mL, and delivered through an IV administration set with a 0.2- or 0.22-µm in-line filter. A volume of IV solution equal to the volume of durvalumab to be added to the IV bag must be removed from the bag prior to the addition of durvalumab. The required volume of durvalumab is then added to the IV bag such that final concentration is within

1 to 20 mg/mL. Mix the bag by gently inverting to ensure homogeneity of the dose in the bag.

If in-use storage time exceeds these limits, a new dose must be prepared from new vials. Infusion solutions must be allowed to equilibrate to room temperature prior to commencement of administration.

No incompatibilities between durvalumab and polyvinylchloride or polyolefin IV bags have been observed.

Dose calculation of durvalumab

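### Section 2.5.1 calls for weight-based dosing at 30 kg or less, but no dosing table, preparation section or eligibility criterion carries that rule or says what the weight-based schedule is.

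*Combined protocol and SAP*

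**What the plan says.** Protocol 2.5.1 justifies the move from per-kg to fixed dosing and then limits it: "Fixed dosing of durvalumab and tremelimumab is recommended only for patients with > 30kg body weight due to endotoxin exposure". For the remaining patients it says: "Patients with a body weight less than or equal to 30 kg should be dosed using a weight-based dosing schedule". The same section gives the equivalence behind the fixed doses: "Based on average body WT of 75 kg, a fixed dose of 1500 mg Q4W durvalumab (equivalent to 20 mg/kg Q4W"). It matches the other drug in the same way, setting its 75 mg dose equal to 1 mg/kg. The pharmacokinetic simulations in support started at 40 kg: "A total of 1000 patients were simulated using body WT distribution of 40–120 kg".

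The sections that sites dose from give milligram amounts only:

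- Section 1.0: "patients will receive the combination of tremelimumab (75 mg IV infusion) and durvalumab (1500 mg IV infusion) on Day 1 for 4 cycles".
- The schema notes: "Tremelimumab: 75 mg IV infusion on" Day 1 of Cycles 1 to 4, and durvalumab 1500 mg in Cycles 1 to 24.
- Table 4: 75 mg and 1500 mg.
- Tables 5 and 6: the same starting doses, with 750 mg and 40 mg as reduced doses.
- Section 9.2.3: "A dose of durvalumab (1500mg) will be administered using an IV bag". Section 9.1.4 does the same for tremelimumab 75 mg. The worked volumes cover only the four fixed amounts.

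Section 7.1 sends the reader to Section 9 for preparation and to Table 7 for dose levels, not to 2.5.1. Sections 4.1 and 4.2 set an age limit but no weight limit. Height and weight are required before entry (Table 1). Table 2 has no weight item, and its vital-signs footnote lists temperature, blood pressure, pulse and respiratory rate.

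**The concern.** A dosing rule with a stated safety reason appears in the background chapter and nowhere in the instructions used to prescribe and prepare the drugs. Nor can it be carried out as written: 2.5.1 gives the per-kg equivalents of the fixed doses at 75 kg, but does not say what the weight-based schedule is. A pharmacist working from Table 4 and Section 9 would have no cue that an exception exists.

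Two things are at stake. First, an eligible patient of 30 kg or less could be dosed in a way that 2.5.1 advises against. Second, the status of that dose is unclear. Section 10.1 defines an overdose as a dose above what the protocol specifies. Section 10.4.2 refers to the Investigator's Brochure unless the protocol specifies otherwise, and requires any overdose to be reported within 24 hours, with or without symptoms. Read against Table 4, 1500 mg and 75 mg are the specified doses; read against 2.5.1, they are not the intended ones for this patient.

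**Working it through.** **Inputs.** Starting doses 1500 mg and 75 mg (2.5.1, Table 4); reduced doses 750 mg and 40 mg (Tables 5 and 6, 9.1.4, 9.2.3); stated equivalents 20 mg/kg and 1 mg/kg at a 75 kg average weight, and the 30 kg limit (all 2.5.1).

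**Reproducing the stated equivalents.** 1500/75 = 20 mg/kg and 75/75 = 1 mg/kg. Both agree exactly.

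**Formula.** Nominal dose per kg = fixed dose / weight. Ratio to the stated equivalent = (1500/weight)/20 for durvalumab and (75/weight)/1 for tremelimumab. Both reduce to 75/weight.

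| Weight | Durvalumab 1500 mg | Tremelimumab 75 mg | Ratio, both drugs |
|---|---|---|---|
| 75 kg | 20 mg/kg | 1 mg/kg | 1.0 |
| 40 kg | 37.5 mg/kg | 1.875 mg/kg | 1.875 |
| 30 kg | 50 mg/kg | 2.5 mg/kg | 2.5 |
| 28 kg | 53.6 mg/kg | 2.68 mg/kg | 2.68 |
| 25 kg | 60 mg/kg | 3 mg/kg | 3.0 |

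The ratio rises as weight falls, so it is at least 2.5 at every weight of 30 kg or less.

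**Reduced doses at 30 kg, against the same equivalents.** Durvalumab: 750/30 = 25 mg/kg, and 25/20 = 1.25. Tremelimumab: 40/30 = 1.33 mg/kg, a ratio of 1.33.

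**What the ratio does not measure.** It is already 1.875 at 40 kg, where 2.5.1 recommends fixed dosing and the simulations cover it. A ratio above 1 is therefore not in itself a breach; the inconsistency lies in the 30 kg limit. Section 2.5.1 reports a weight coefficient of at most 0.5. If that is a power exponent on clearance (an assumption; the protocol does not say), and if it holds below the simulated range, exposure at 30 kg on the fixed dose relative to a 75 kg patient would lie between (75/30)^0 = 1.0 and (75/30)^0.5 = 1.58. No endotoxin content or threshold is given, so the stated reason for the limit cannot be quantified.

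**The case against.** The best defence is that this is an uncarried exception. Section 2.5.1 is protocol text and states the exception explicitly. Table 4 gives the general dose, and nowhere is a site told to disregard weight. Weight is known at entry, a history and physical is required before each cycle, and adults with ECOG 0 or 1 will hardly ever weigh 30 kg or less. The source wording is also advisory in tone.

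Much of this stands. It limits the reach of the point and rules out three stronger readings that a reader might infer:

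- *That such patients would be over-exposed 2.5-fold.* The documents do not support this. The figure is a nominal mg/kg ratio at the starting dose, 2.5.1 reports only a minor weight effect on pharmacokinetics, and the limit rests on endotoxin, for which no figure is given.
- *That such a dose would be recorded as given per protocol.* This is not established. Since 2.5.1 is part of the protocol, the dose could equally be a reportable overdose under 10.1; 10.4.2 also depends on a brochure outside these documents.
- *That a low-weight patient would go unnoticed.* At entry this is wrong, because Table 1 requires weight. After entry, weight may be taken at the physical examination, but Table 2 does not ask for it.

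The defence does not show that the rule can be followed. With no schedule specified and no pointer from the operative sections, a site that follows Table 4 and Section 9 faithfully departs from 2.5.1.

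**Conclusion.** The inconsistency is real and minor. The operative dosing text conflicts with a rule that the same protocol states for a safety reason, and the rule has no schedule to implement it. For a patient of 30 kg or less dosed from Table 4 and Section 9, the starting dose is at least 2.5 times the nominal per-kg equivalent in 2.5.1, and at 30 kg the reduced doses are 1.25 and 1.33 times it. This rests on the stated equivalents at 75 kg and on the site not applying 2.5.1 independently.

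The documents give no weight distribution, so the number affected cannot be calculated; among 12 to 21 evaluable adults with ECOG 0 or 1 it is likely to be none or very few. Nothing here shows an effect on the response rate, the stopping rule or the safety tables.

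**What to change.** Reconcile 2.5.1 with Section 4, Table 4, Tables 5 and 6 and Section 9, and align the overview and schema, so that one consistent instruction applies to patients of 30 kg or less. It should also cover patients whose weight falls to that level on study, and the text should say whether weight is to be recorded after entry, since Table 2 does not list it. Once the instruction is settled, make clear how 10.1 and 10.4.2 apply to a fixed dose given at or below 30 kg. Which rule applies is the sponsor's clinical decision. The cost is a wording amendment, with no change to sample size, stopping rule or analysis.

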2.9 Translational opportunities

Pre-clinical and clinical data suggest that combination of immune checkpoint inhibitors targeting non-overlapping pathways such as durvalumab and tremelimumab may induce synergistic effect leading to improved tumor response in comparison to monotherapy with either agent alone. We hypothesize that the combination of radiation and dual immune checkpoint blockade with durvalumab plus tremelimumab may have synergistic effect on effector T cell activation ([Pardoll 2012](#)).

This study serves as a platform allowing for detailed assessment of the mechanisms of immune stimulation, predictive markers of response or resistance and rational development of the next generation of combination immunomodulatory interventions ([Taube 2014](#), [Topalian 2012](#)). Samples will be collected that may be used in post-hoc analyses including but, not limited to:

- peripheral lymphocytes analysis for immune cell gene expression and quantitative changes of lymphocyte subpopulation and immune-related cells.
- collection of tumor tissues from unirradiated tumor sites prior to radiation and after two cycles of therapy for further analysis of immune response in tumor.
- analysis of gene expression related to immune checkpoint pathways.
- analysis of frequency of mutation-associated neoantigens in tumor tissues.

3.0 **STUDY AIMS AND ENDPOINTS**

3.1 **Primary aim and endpoint**

Aim: To determine the efficacy of the dual immune checkpoint blockade with durvalumab plus tremelimumab following a small dose of hypofractionated palliative radiation in patients with MSS mCRC who have progressed on chemotherapy.

Endpoint: Overall objective response rate (ORR) as measured by RECIST 1.1 criteria.

3.2 **Secondary aims and endpoints**

3.2.1 ***Clinical benefit rate***

Aim: To determine objective tumor decrease and stable disease (SD) at 16 weeks.

Endpoint: Measurement of disease status by continuous tumor measurement (any partial response [PR], any complete response [CR] and SD at 16 weeks).

3.2.2 ***Duration of response***

Aim: To determine the duration of response of mCRC to study therapy.

Endpoint: Measurement of time from study entry until documentation of progression as determined by RECIST 1.1.

3.2.3 ***Safety and Toxicity***

Aim: To determine the safety of the combination of dual immune checkpoint blockade with durvalumab plus tremelimumab following hypofractionated palliative radiation in patients with MSS mCRC who have progressed on chemotherapy.

Endpoint: Frequency and severity of adverse events categorized using the NCI Common Terminology Criteria for Adverse Events version 4.0 (CTCAE v4.0).

3.3 **Exploratory Translational Science**

Aim: To explore the effect of the combination of dual immune checkpoint blockade with durvalumab plus tremelimumab following hypofractionated palliative radiation on immune response in blood and in tumor tissue.

Aim: To correlate the frequency of mutation-associated neoantigens in tumor tissues and clinical response.

4.0 PATIENT ELIGIBILITY AND INELIGIBILITY

4.1 Conditions for patient eligibility

A patient cannot be considered eligible for this study unless all of the following conditions are met:

- 4.1.1 The patient must have consented to participate and, prior to beginning specific study procedures, must have signed and dated an appropriate IRB-approved consent form that conforms to federal and institutional guidelines for study treatment and for submission of tumor and blood samples as required by FC-9 correlative science studies (see [Section 6.0](#)).
- 4.1.2 Patients must be ≥ 18 years old.
- 4.1.3 The ECOG performance status must be 0 or 1 (see [Appendix A](#)).
- 4.1.4 There must be histologic confirmation of a diagnosis of colorectal adenocarcinoma.
- 4.1.5 The tumor must have been determined to be microsatellite stable (MSS).
- 4.1.6 There must be documentation by PET/CT scan, CT scan, or MRI, that the patient has evidence of measurable metastatic disease per RECIST 1.1.
- 4.1.7 Patients must have an accessible metastatic lesion for pretreatment core biopsy.
- 4.1.8 Unless either drug is medically contraindicated, patients must have received oxaliplatin and irinotecan as part of standard metastatic chemotherapy regimens.
- 4.1.9 The patient must have multiple sites of metastatic disease with at least one lesion amenable to treatment with stereotactic radiation therapy (SBRT) in the lung or liver and at least one lesion not being irradiated and meeting RECIST 1.1. (See [Appendix B](#)).
- 4.1.10 At the time of study entry, blood counts performed within 2 weeks prior to study entry must meet the following criteria:
 - ANC must be $\geq 1500/\text{mm}^3$,
 - Platelet count must be $\geq 100,000/\text{mm}^3$; and
 - Hemoglobin must be ≥ 9 g/dL.
- 4.1.11 The following criteria for evidence of adequate hepatic function performed within 2 weeks prior to study entry must be met:
 - Total bilirubin must be $\leq 1.5 \times \text{ULN}$ (upper limit of normal) for the lab unless the patient has a bilirubin elevation $> 1.5 \times \text{ULN}$ to $3 \times \text{ULN}$ due to Gilbert's disease or similar syndrome involving slow conjugation of bilirubin; *and*
 - AST and ALT must be $\leq 2.5 \times \text{ULN}$ for the lab *with the following exception*: for patients with documented liver metastases, AST and ALT must be $\leq 5 \times \text{ULN}$.
- 4.1.12 Adequate renal function within 4 weeks prior to study entry, defined as serum creatinine $\leq 1.5 \times \text{ULN}$ for the lab or measured or calculated creatinine clearance > 40 mL/min by Cockcroft-Gault formula.
- 4.1.13 All hematologic, gastrointestinal, and genitourinary chemotherapy toxicities must be $< \text{Grade } 2$ at the time study therapy is to begin. (Note: Transfusions may be used to correct hemoglobin for patients experiencing anemia from therapy who otherwise would be eligible for the study.)
- 4.1.14 Patients with reproductive potential (male/female) must agree to use accepted and highly effective methods of contraception while receiving study therapy and for at least

6 months after the completion of study therapy. The definition of effective method of contraception will be based on the investigator's discretion. See [Appendix C](#). Female patients must either be of non-reproductive potential (i.e., post-menopausal by history: ≥ 60 years old and no menses for ≥ 1 year without an alternative medical cause; OR history of hysterectomy, OR history of bilateral tubal ligation, OR history of bilateral oophorectomy) or must have a negative serum pregnancy test upon study entry.

4.2 Conditions for patient ineligibility

Any patient with one or more of the following conditions will be ineligible for this study:

- 4.2.1 Diagnosis of anal or small bowel carcinoma.
- 4.2.2 Colorectal cancer other than adenocarcinoma, e.g., sarcoma, lymphoma, carcinoid.
- 4.2.3 Previous therapy with any PD-1 or PD-L1 inhibitor including durvalumab or anti-CTLA4 (including tremelimumab) for any malignancy.
- 4.2.4 Receipt of live attenuated vaccination within 30 days prior to study entry or within 30 days of receiving study therapy.
- 4.2.5 Active or chronic hepatitis B or hepatitis C.
- 4.2.6 Symptomatic or uncontrolled brain metastases requiring concurrent treatments, uncontrolled spinal cord compression, carcinomatous meningitis, or new evidence of brain or leptomeningeal disease; uncontrolled seizures.
- 4.2.7 Active infection or chronic infection requiring chronic suppressive antibiotics.
- 4.2.8 Active or documented inflammatory disease.
- 4.2.9 Known history of human immunodeficiency virus (HIV) or acquired immunodeficiency-related (AIDS) illnesses.
- 4.2.10 Current or prior use of immunosuppressive medication within 28 days before the first dose of study therapy with the exceptions of intranasal corticosteroids or systemic corticosteroids at physiological doses that do not exceed 10mg/day of prednisone or an equivalent corticosteroid.
- 4.2.11 History of allogeneic organ transplantation.
- 4.2.12 Any of the following cardiac conditions:
 - Documented NYHA Class III or IV congestive heart failure,
 - Myocardial infarction within 6 months prior to study entry,
 - Unstable angina within 6 months prior to study entry,
 - Symptomatic arrhythmia.
- 4.2.13 Uncontrolled high blood pressure defined as systolic BP ≥ 150 mmHg or diastolic BP ≥ 100 mmHg with or without anti-hypertensive medication. Patients with initial BP elevations are eligible if initiation or adjustment of BP medication lowers pressure to meet entry criteria.
- 4.2.14 Active or prior documented inflammatory bowel disease (e.g., Crohn's disease, ulcerative colitis).
- 4.2.15 Ongoing or active gastritis or peptic ulcer disease.

- 4.2.16 Active bleeding diatheses.
- 4.2.17 Known history of previous diagnosis of tuberculosis.
- 4.2.18 History of hypersensitivity to durvalumab or tremelimumab or any excipients of these drugs.
- 4.2.19 Known history or confirmation of active pneumonia, pneumonitis, symptomatic interstitial lung disease, or definitive evidence of interstitial lung disease described on CT scan, MRI, or chest x-ray in asymptomatic patients; dyspnea at rest requiring current continuous oxygen therapy.
- 4.2.20 Active or prior documented autoimmune disease or inflammatory condition requiring ongoing immunosuppressive medications. (Note: Patients with vitiligo, Grave disease, or psoriasis not requiring systemic treatment within the past 2 years are eligible.)
- 4.2.21 Other malignancies unless the patient is considered to be disease-free and has completed therapy for the malignancy \geq 12 months prior to study entry. Patients with the following cancers are eligible if diagnosed and treated within the past 12 months: carcinoma in situ of the cervix, and basal cell and squamous cell carcinoma of the skin.
- 4.2.22 Psychiatric or addictive disorders or other conditions that, in the opinion of the investigator, would preclude the patient from meeting the study requirements or interfere with interpretation of study results.
- 4.2.23 Pregnancy or lactation at the time of study entry. (Note: Pregnancy testing should be performed within 14 days prior to study entry according to institutional standards for women of childbearing potential.)
- 4.2.24 Use and/or receipt of the last dose of anti-cancer therapy (i.e., chemotherapy, immunotherapy, endocrine therapy, targeted therapy, biologic therapy, tumor embolization, monoclonal anti-bodies) within 14 days prior to the first dose of study therapy. (Note: SBRT is required prior to beginning study therapy.)
- 4.2.25 Use of any investigational agent within 4 weeks of starting study therapy.

